### **2.3 Endpoints**

#### **2.3.1 Safety Endpoints**

Safety variables will be assessed by the following evaluations:

- Adverse events and serious adverse events
- Incidence of AEs of hypocalcemia (eg, paresthesia, numbness, tetany) and hypercalcemia (eg, constipation, nausea, poor appetite or vomiting, frequent urination, thirst, and kidney stones)
- Incidence of hypercalciuria
- Laboratory test results
  - Hematology (hematocrit, hemoglobin, white blood cells, red blood cells, platelets, differential)
  - Serum chemistries (standard Chem-20 panel, including calcium, phosphate, and albumin)
  - Serum 25(OH) vitamin D levels
  - Serum 1,25-dihydroxyvitamin D levels
  - Creatinine clearance
  - Serum bone turnover markers
  - Urinalysis
  - 24-hour urine calcium, phosphate, sodium, and creatinine excretion
  - PTH and *E. coli* protein (ECP) antibodies
- Bone mineral density by dual-energy x-ray absorptiometry (DXA)

- Electrocardiogram (ECG) parameters
- Physical examinations (including vital signs)
- Reason for termination from the study
- Immunogenicity analysis (AEs and SAEs related to PTH antibodies)
- Injection pen-related events and/or complaints

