**Table 6-3 Schedule of Evaluations and Procedures – Long-term Extension after Month 36**

Study Procedures	Proposed Study Month a	Months 38/50/62	Months 40/52/64	Months 42/54/66/74	Months 44/56/68/76	Months 46/58/70/78	Months 48/60/72/80	End of Treatment b	4 weeks F/up Phone c
Visit Windows		± 2 weeks	± 2 weeks	± 2 weeks	± 2 weeks	± 2 weeks	± 2 weeks	± 1 week	± 7 days
Re-consent subject d		X							
Concomitant medications		X	X	X	X	X	X	X	
Adverse event monitoring, including pen-related events/complaints		X	X	X	X	X	X	X	X
Assessment of clinical episodes of hypocalcemia and hypercalcemia		X	X	X	X	X	X	X	
Physical examination e				X e			X d	X	
Vital signs f and weight		X	X	X	X	X	X	X	
Electrocardiogram (12-lead)								X g	
Bone mineral density by DXA h							X	X i	
Hematology j							X	X	
Serum chemistry (20-panel) j							X	X	
Serum calcium (local)*									
Serum calcium, phosphate		X	X	X	X	X	X	X	
Serum calcium, potassium, sodium k		X	X	X	X	X	X	X	
Serum 25-hydroxyvitamin D		X	X	X	X	X	X	X	
Serum 1,25-dihydroxyvitamin D				X			X	X	
Serum bone turnover markers			X		X		X	X	
Creatinine clearance (estimated GFR)			X		X		X	X	
PTH and ECP antibodies l				X			X	X m	
Serum pregnancy test (WOCBP only)								X	
Urine pregnancy test (WOCBP)		X	X	X	X	X	X		
Urinalysis								X	
24-hour urine calcium, phosphate, sodium, creatinine			X		X		X	X	
Diary review n		X	X	X	X	X	X	X	
Dispense/administration/accountability of study drug, and pen injectors/ancillary supplies o		X	X	X	X	X	X	X	
Collect used/unused study drug / pen injectors p		X	X	X	X	X	X	X	

DXA = dual-energy x-ray absorptiometry; ECP = *E. coli* protein; EoT = end of treatment; F/up = follow up; GFR = glomerular filtration rate; Int.= interim visit; PTH = parathyroid hormone; WOCBP = women of child-bearing potential

NOTE: Following Month 72, the every 2-month visit schedule will repeat (ie, visits procedures for Month 74 will repeat starting with those shown at Months 26/38/50.)

\*Any adjustment of study drug or oral calcium and active vitamin D doses requires testing of total serum calcium concentrations at interim time points.

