#### **6.4.5 Long-term Extension Visits**

Subjects who continue into the long-term extension will have the following evaluations performed every 2 months unless otherwise indicated:

- Record any change in concomitant medications on the appropriate concomitant medication eCRF, including dose and frequency.
- Adverse event evaluation/update, including any incidences of hypocalcemia or hypercalcemia
- Urine pregnancy test (WOCBP only)
- Brief physical examination (every 6 months)
- Vital signs measurements (prior to blood draws) and weight
- Blood samples for serum chemistries and hematology (every 12 months)
- Blood samples for creatinine clearance and bone turnover markers (every 4 months)
- Local total serum calcium (as needed)
- Blood sample for PTH and ECP antibodies (predose) (every 6 months)
- Serum calcium and phosphate

- Serum 25(OH) vitamin D
- Serum 1,25-dihydroxyvitamin D (every 6 months)
- 24-hour urine calcium, phosphate, sodium, and creatinine (every 4 months)
- A BMD test by DXA (every 12 months)
- If calcium-sparing diuretics are instituted and/or the dose subsequently changed, monitoring for serum potassium, sodium, and calcium will be done 1 week and again 1 month later and then at each subsequent scheduled clinic visit.
- Review the subject's diary to assess compliance to protocol procedures and dosing/supplement regimens. Subjects will complete the diary for the 2-week period prior to the scheduled study visit. If the subject does not record the diary information as indicated during this time period, he/she may record it during the 2 weeks following the visit. This information will then be reviewed with the subject by phone or at the next scheduled visit.
- Collect used and unused drug cartridges and pen injectors for assessment of accountability.
- Subjects will be provided with the following study supplies:
  - Study medication cartridges in sufficient number to supply daily doses until the next scheduled clinic visit
  - Ancillary injection supplies (ie, alcohol swabs, needles, etc.)
  - Calcium (carbonate or citrate) supplements in sufficient quantity to supply daily doses until the next scheduled clinic visit through approximately May 2014. Following this date, only calcium citrate will be provided.
  - Collection container for 24-hour urine

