3.1. General Description

This study is a long-term, open-label study using rhPTH[1-84] for the treatment of adults with hypoparathyroidism. Subjects can enroll if they either previously completed the NPSP558 RELAY study (PAR-C10-007) (8 weeks of active therapy) and/or completed the REPLACE study (CL1-11-040) (Visit 18).

The goal of this study is to optimize rhPTH[1-84] dosing while reducing calcitriol and oral calcium (carbonate or citrate) supplementation to as low as safely possible and maintaining total serum calcium levels. Dose adjustments to rhPTH[1-84] and to the calcium/calcitriol supplements and safety monitoring of calcium levels are explained in protocol Appendix 2, rhPTH[1-84] and Supplement Titration Guideline.

- The starting dose of rhPTH[1-84] for this study will be 25 or 50 µg SC once daily (QD)
- Subjects may have their rhPTH[1-84] dose adjusted by the investigator at any time during the study, with the goal of achieving or maintaining total serum calcium levels in the range of 8.0 to 9.0 mg/dL.
- If **ANY** predose (trough) total serum calcium is >11.9 mg/dL study drug will be stopped.
- Subjects will have blood draws to assess total serum calcium levels (which may be performed locally) 3 to 5 days after **ANY** dose adjustment of rhPTH[1-84], after any significant change in doses of calcium and/or calcitriol supplements, or at any other time at the discretion of the investigator.
- Study visits during the first 12 months of the study will be conducted at Weeks 1 (baseline), 4, 8, and then every 8 weeks thereafter up to Week 48 (Visit 8). The Week 52 visit (Visit 9) is scheduled 4 weeks later.
- At any time following the Week 16 (Visit 4), subjects who are on a stable dose of rhPTH[1-84] and have a 24-hour urine calcium >300 mg (males) and >250 mg (females) may be treated for hypercalciuria with calcium-sparing diuretics, if this therapy had not been introduced prior to the study.
- At the end of Week 52, subjects will be invited to extend their study drug regimen until January 2018 or after the completion of the last patient's Month 72 visit, whichever comes last..
- During this time, subjects will return to the clinic for interim visits every 2 months (Months 14, 16, 18, etc).

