5.4.3. Handling of Partial Dates

Complete dates will be imputed from partial dates of adverse events and medications solely for the purpose of defining treatment emergence for adverse events and prior/concomitant status for medications. Dates will be defined using the hierarchy of derivations below.

Adverse event or medication start date:

1. If year and month are known, and it is the month and year of the first dose date, use the first dose date.
2. If year and month are known, and it is the month and year of the informed consent, use the informed consent date.
3. If year and month are known, and the month is not the month and year of the first dose or informed consent, use the first day of the month.
4. If only year is known, and it is previous to the year of the informed consent, use June 30th of that year.
5. If only year is known, and it is the year of the informed consent, use the informed consent date.
6. Should any of the previous start dates created be after a complete stop date provided, use the stop date instead of the date that would otherwise be created.
7. Otherwise, if start date is unknown leave as missing.

Medication stop date:

1. If year and month are known and study medication stopped during that month and year, use the stop date of study medication.
2. If year and month are known and informed consent was provided during that month and year, use the date of informed consent.
3. If year and month are known and study medication stopped after the date of informed consent and not in the month that medication stopped, use the last day of the month.
4. If year and month are known and are prior to the month of informed consent, use the first day of the month.
5. If only year is known and study medication stopped during that year, use the stop date of study medication.
6. If only year is known and study medication stopped after that year, use December 31st of that year.
7. If only year is known and study medication stopped prior to that year, use the first day of the year.
8. Should any of the previous stop dates created be before a start date, either a complete date or an imputed one, use the (imputed) start date instead of the date that would otherwise be created.
9. Otherwise, if stop date is unknown leave as missing.

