6.8.1. Adverse Events

Adverse events will be coded using MedDRA Version 13.0. Adverse event listings will provide the verbatim term as well as SOC and PT for each recorded event. A separate listing may be produced to provide the SOC, high level term, PT, and lower level term that are associated with each verbatim term.

Treatment emergent adverse events (TEAEs) are defined as AEs whose onset occurs, severity worsens or intensity increases after receiving the study medication of this study and ≤ 30 days after last dose of study drug. If any AE records contain only partial dates, these will be handled by imputation, as described in Section 7.4.3. AEs which are not treatment emergent will be flagged in listings.

An overview of TEAEs will be summarized using the number and percentage of subjects. The number of events will also be presented except for summaries by highest category. Categories summarized will include any TEAEs, severity of TEAEs (any and highest category), relationship of TEAEs to treatment (any and highest category), treatment emergent serious AEs (TESAEs), severity of TESAEs, relationship of TESAEs to treatment, TEAEs leading to discontinuation, and TEAEs leading to death.

Treatment emergent AEs will be summarized using number and percentage of subjects. Subject incidence for AEs within each SOC and PT will be presented, and the number of events will also be summarized except for summaries by highest category. Categories summarized will be the same as those summarized overall, except that no summary table will be provided for TEAEs leading to death.

Summaries of TEAEs and TESAEs will also be presented by PT. These presentations will be sorted by descending incidence.

Listings will be provided for serious adverse events (SAEs), AEs leading to discontinuation, and AEs leading to deaths.

The incidence of hypocalcemia and hypercalcemia will be identified by clinical preview. Prevalence of hypocalcemia and hypercalcemia will be assessed at all visits on the date of visit. The number of subjects with hypocalcemia and hypercalcemia and the number of episodes of hypocalcemia and hypercalcemia will be assessed for the overall trial.

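### Hypo- and hypercalcemia AEs are shown over time only as prevalence on the visit date, so no planned output gives episode frequency by period as the protocol synopsis commits

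*SAP*

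**What the plan says.** Protocol 2.3.1 names as a safety endpoint "Incidence of AEs of hypocalcemia (eg, paresthesia, numbness, tetany) and hypercalcemia", and the primary objective (Protocol 2.1) is long-term safety and tolerability.

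Collection is continuous. Protocol Table 6-3 has a row at every extension visit for "Assessment of clinical episodes of hypocalcemia and hypercalcemia", and Protocol 6.4.5 asks at those visits for "Adverse event evaluation/update, including any incidences of hypocalcemia or hypercalcemia". Protocol 6.2.1.3 has start and stop dates recorded for each AE.

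SAP 6.8.1 then plans three things for these events. They are to be identified through a clinical look at the data, for which no table or time axis is given. "Prevalence of hypocalcemia and hypercalcemia will be assessed at all visits on the date of visit". And "The number of subjects with hypocalcemia and hypercalcemia and the number of episodes of hypocalcemia and hypercalcemia will be assessed for the overall trial".

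The safety analysis paragraph of the protocol synopsis says that safety data, with the frequency of hypo- and hypercalcemia AEs listed by name, will be summarized by when they were collected. Protocol 8.2 says the same of AEs in general. SAP 3.4.2 states that no protocol-specified analysis is changed.

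**The concern.** Prevalence on a visit date and frequency since the last visit are different quantities. The first counts a subject only if an event is ongoing on the day of the visit. The second counts every event that began since the previous visit, which is what the sites are asked to collect. With visits about two months apart, an episode that starts and stops between two visits adds to the overall total but has no place on the time axis.

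At stake is the reading of a named safety endpoint in a study extended to as much as 80 months of treatment. The overall total pools the early period of dose adjustment with years of later treatment, and no person-time denominator is stated for it although subjects may leave at different times. It cannot show whether episodes become rarer, persist or become more common.

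**Working it through.** The documents state no episode rate, duration or prevalence, so there is no figure to reproduce. The check asks what share of episodes the visit-date rule can show, over assumed durations.

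**Inputs**
- Extension spacing, g: SAP 3.1 says "During this time, subjects will return to the clinic for interim visits every 2 months (Months 14, 16, 18, etc". 2 × 365.25/12 = 60.9, taken as 61 days.
- Year 1 spacing: SAP 3.1 says "Study visits during the first 12 months of the study will be conducted at Weeks 1 (baseline), 4, 8, and then every 8 weeks", up to Week 48, then Week 52. Of the eight gaps, three are 28 days (baseline to Week 4, Week 4 to 8, Week 48 to 52) and five are 56 days.
- Subjects: about 50 (SAP 3.3).
- Episode duration d and episode rate r per subject-year: assumptions, shown as ranges.

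**Step 1. Share of episodes present on a visit date.** If onset is unrelated to visit dates, the share is min(1, d/g). For example, 3/61 = 4.9% and 7/28 = 25.0%.

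| Duration d | g = 28 | g = 56 | g = 61 |
|---|---|---|---|
| 1 day | 3.6% | 1.8% | 1.6% |
| 3 days | 10.7% | 5.4% | 4.9% |
| 7 days | 25.0% | 12.5% | 11.5% |
| 14 days | 50.0% | 25.0% | 23.0% |
| 30 days | 100% | 53.6% | 49.2% |

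**Step 2. What each measure would report at an extension visit.** With Poisson onsets and fixed duration, expected visit-date prevalence is 1 − exp(−r·d/365.25). The expected share of subjects with at least one onset in the interval is 1 − exp(−r·61/365.25).

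| r per year | d | Prevalent on visit date | Onset in interval |
|---|---|---|---|
| 1 | 3 days | 0.8% (0.4 of 50) | 15.4% (7.7 of 50) |
| 1 | 7 days | 1.9% (0.9 of 50) | 15.4% (7.7 of 50) |
| 2 | 30 days | 15.1% (7.6 of 50) | 28.4% (14.2 of 50) |
| 4 | 14 days | 14.2% (7.1 of 50) | 48.7% (24.4 of 50) |

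The visit-date figure depends on rate times duration. A change over time in episode length would therefore move it even if episodes occurred equally often.

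**Step 3. Does another output fill the gap?**
- The TEAE tables in SAP 6.8.1 count subjects and events by SOC, PT, severity and relationship, with no breakdown by period.
- SAP 6.8.2 summarizes serum chemistry by visit with shift tables. This is a time course, but of laboratory values at scheduled draws. The same section keeps unscheduled results out of the summaries, so the interim calcium checks that Protocol 3.1 requires 3 to 5 days after a dose adjustment appear in listings only.

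Neither gives episode frequency by period.

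**The case against.** The strongest reply is that the endpoint itself is fully analysed. It is incidence, and the overall count of subjects and episodes, together with the TEAE tables, delivers that. This is right, and it confines the point to the time course.

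Second, durations of a few days are assumed. The endpoint also lists symptoms such as constipation, thirst and kidney stones, which may last longer. Protocol 6.2.1.3 lets an AE be recorded as intermittent and asks for a diagnosis rather than each symptom, so recurrent symptoms may form one record that spans several visits and is seen on a visit date. This stands, and it is why the table runs to 30 days.

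Third, the SAP sentence does not say whether a symptom or a laboratory value is meant. For a laboratory value, status on the visit day is a natural measure. But the sentence stands in the adverse event section, and under that reading the AEs would have no display over time at all.

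Two stronger readings are tempting, and the documents support neither. A reader might infer that the by-visit table would be practically empty however often episodes occur. Step 2 shows otherwise: 4 episodes a year of 14 days, or 2 a year of 30 days, give about 14% to 15% prevalence. A reader might also infer that the table cannot be built because SAP 5.4.3 has a rule headed "Medication stop date" and none for AE stop dates. But those rules serve only to define treatment emergence and prior or concomitant status, AE stop dates are collected, and nothing suggests that they will be missing.

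**Conclusion.** The point holds as a gap in the time course only. SAP 6.8.1 replaces the protocol's frequency by time of collection with visit-date prevalence, without declaring a change. At the 61-day extension spacing, about 95% to 98% of episodes lasting 1 to 3 days, 89% of those lasting 7 days, 77% of those lasting 14 days and 51% of those lasting 30 days would not appear in it. At the 28-day gaps in year 1, the shares missed are 96%, 89% and 75% for 1, 3 and 7 days. These figures assume that onset is unrelated to visit dates and that each episode is recorded separately. The true durations and rates are not in the documents.

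The study is descriptive and untested, so no inference is at risk. What is affected is whether the report can say how the frequency of these events changes over long-term treatment, which is worth correcting because the data are already collected.

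**What to change.** In SAP 6.8.1, keep visit-date prevalence as a supplementary display and add, separately for hypocalcemia and hypercalcemia AEs:

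- for each between-visit interval (day after the previous visit through the current visit) or each study year, the number and percentage of subjects in follow-up with at least one AE with onset in that period;
- the number of episodes with onset in that period;
- the rate per subject-year of follow-up in that period.

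Place episodes by AE start date. Extend the existing start-date rules in SAP 5.4.3 to this use, and show on a separate line any episode whose start is left missing under them. State what counts as a separate episode and how a missed visit is treated.

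The cost is a short addition to the SAP and one more descriptive table, with no new data collection. The downside is that episodes with partial start dates may fall in the wrong period, since a date known only to the month is in most cases set to the first day of that month. Yearly periods reduce this and also remove most of the difficulty with missed visits.

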6.8.2. Clinical Laboratory Evaluation

All laboratory parameters will be collected and processed via a central laboratory, with exception of all urine pregnancy tests and total serum calcium levels which will be done at investigator's local laboratories. Standard international (SI) units will be used for data presentation. Only scheduled lab parameters will be included in the lab summaries. All lab data will be included in the listings.

Quantitative results will be summarized for hematology, serum chemistry, thyroid function tests (levothyroxine and thyroid-stimulating hormone), creatinine clearance, urinary chemistries (24-hour urine calcium, phosphate, and sodium excretion), and selected urinalysis parameters (pH, specific gravity, and urobilinogen) by visit. Both actual values and change from baseline will be summarized. Additionally, shift tables will be presented, summarizing cross tabulations of low,

normal, and high based on the parameter normal range, from baseline to each post-baseline visit and EOT. Percentages for shift tables will be based on the number of subjects with both baseline and post-baseline values at each visit.

Categorical urinalysis findings and urine pregnancy results will be presented in appendix data listings only.

Estimated creatinine clearance rate will be re-calculated based on the Cockcroft-Gault (C-G) equation:

$$\text{CLcr (mL/min)} = [140 - \text{age (years)}] \times \text{weight (kg)} \{ \times 0.85 \text{ for female subjects} \} / (72 \times \text{serum creatinine (mg/dL)}),$$

Estimated creatinine clearance rate will be summarized by stages as defined in Table 5.

Table 6.1 Definition of the Stages of Clcr3

Stage	Description	CLcr (mL/min)
1	Control (normal) Glomerular filtration rate (GFR)	≥ 90
2	Mild decrease in GFR	60-89
3	Moderate decrease in GFR	30-59
4	Severe decrease in GFR	15-29
5	End Stage Renal Disease (ESRD)	<15 not on dialysis
		Requiring dialysis

The number and percentage of subjects with post-baseline results qualifying as markedly abnormal will be summarized by parameter. A listing of all values for the parameter which qualifies as markedly abnormal will be provided. Markedly abnormal laboratory criteria are defined in Table 6.

Table 6.2 Markedly Abnormal Laboratory Criteria⁴

Lab parameter	Unit	Lower Limit	Upper Limit
Chemistry			
Albumin	g/L	≤20	≥90
Alkaline Phosphatase	U/L	NA	>2*ULN
ALT	U/L	NA	>3*ULN
Amylase	U/L	≤15	≥350
AST	U/L	NA	>3*ULN
Bilirubin	μmol/L	NA	>2*ULN
BUN	mmol/L	NA	≥10.7
Calcium (total)	mmol/L	≤2.1	≥3.0
Chloride	mmol/L	≤80	≥125
Cholesterol (total)	mmol/L	NA	≥12.9
Creatinine	μmol/L	NA	≥177
Creatinine clearance	ml/min	≤60	NA

Glucose	mmol/L	<=1.7	>=13.9
Gamma glutamyl transferase	U/L	NA	>=100
Phosphate	mmol/L	NA	>=2
Potassium	mmol/L	<=2.5	>=6.5
Sodium	mmol/L	<=120	>=165
Triglycerides	mmol/L	NA	>=5.6
Uric acid	μmol/L	NA	>=624 (males) >=505 (females)
Hematology			
Hematocrit	L/L	<=0.37 (males) <=0.32 (females)	>0.54 (males) NA (females)
Hemoglobin	g/L	<=115 (males) <=95 (females)	NA
Platelets	10 ⁹ /L	<=75	>=700
RBC count	10 ¹² /L	<=2.5 (males) <=2.0 (females)	NA
WBC count	10 ⁹ /L	<=2.8	>=16.0
Basophils	L/L	NA	>=0.15
Eosinophils	L/L	NA	>=0.10
Lymphocytes	L/L	NA	>=0.80
Monocytes	L/L	NA	>=0.40
Neutrophils	L/L	<=0.15	NA
24-Hour urine			
Urine calcium	mg	NA	>300 for men >250 for women

NA=Not Applicable; ULN = Upper Limit of Normal

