### Challenges Associated With Oral Calcium Therapy

The US Institute of Medicine/National Academy of Sciences daily Dietary Reference Intake for calcium for individuals aged 18 to 70 years is 1000 to 1200 mg/day, while the daily Tolerable Upper Intake level (level at which there is no likely risk of adverse events [AEs]) is 2500 mg/day for adults. Patients with hypoparathyroidism typically require supplemental oral calcium therapy at or higher than this recommended limit, typically ranging between 2000 and 3500 mg/day. Impaired regulation of calcium and phosphate homeostasis due to a lack of PTH and pharmacological treatment with vitamin D metabolites/analogues combine with high oral calcium intake to increase the likelihood of soft tissue deposition of calcium salts. These can occur in the brain (ie, basal ganglia), kidneys, ocular lens, and other organs leading to structural damage and

a loss of function, as seen in premature cataracts, and even Parkinsonism. Without PTH to help conserve the filtered calcium in the kidney, substantial amounts of calcium can be lost leading to hypercalciuria with the attendant risks of nephrocalcinosis, hematuria and renal dysfunction. Thiazide diuretics such as hydrochlorothiazide may be used to stimulate the reabsorption of calcium in the distal nephron. In cases of profound hypocalcemia patients often require treatment with IV calcium along with cardiac monitoring. Some patients may require a permanent catheter placement for IV access.

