### 4.2 Inclusion Criteria

Subjects who meet all the following inclusion criteria can be enrolled into this study:

1. Signed and dated informed consent form (ICF) before any study-related procedures are performed
2. Previously completed the NPSP558 RELAY study 8 weeks of active therapy and/or previously completed the NPSP558 REPLACE study (Visit 18)
3. Able to perform daily SC self-injections of study medication (or have designee perform injection) via a multidose pen injector into the thigh
4. Willingness and ability to understand and comply with the protocol
5. Women who are: (1) postmenopausal defined as 12 months amenorrhea with appropriate serum follicle stimulating hormone (FSH) levels ( $> 40$  IU/L); (2) surgically sterilized; OR (3) of childbearing potential with a negative pregnancy test at screening and who consent to use two acceptable methods of contraception for the duration of the study, with pregnancy testing at every scheduled visit. Male subjects who have female partners of childbearing potential together also must use 2 acceptable forms of contraception during the subject's participation in the study.
6. Serum creatinine  $< 1.5$  mg/dL at enrollment
7. Total serum calcium  $\leq$  ULN based on local laboratory result prior to enrollment

8. Serum 25(OH) vitamin D  $\leq$  1.5 times the ULN within approximately 16 weeks prior to enrollment

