6.8.4.1. Vital Signs

Vital signs to be analyzed include sitting blood pressure, sitting heart rate, and body temperature.

Observed vital signs and changes from baseline will be summarized by visit.

The number and percentage of subjects with post-baseline results qualifying as markedly abnormal will be summarized by parameter. A listing will present all values for a subject and parameter for cases where at least one value for that parameter was markedly abnormal. Post-baseline markedly abnormal vital signs criteria are defined in Table 8.

Table 6.4 Markedly Abnormal Post-Baseline Vital Signs⁷

Vital Sign Parameter	Abnormally Low	Abnormally High
Systolic blood pressure (mmHg)	A decrease from Baseline of ≥ 20 to a value ≤ 90	An increase from Baseline of ≥ 20 to a value ≥ 180
Diastolic blood pressure (mmHg)	A decrease from Baseline of ≥ 15 to a value ≤ 50	An increase from Baseline of ≥ 15 to a value ≥ 105
Heart Rate (bpm)	A decrease from Baseline of ≥ 15 to a value ≤ 50	An increase from Baseline of ≥ 15 to a value ≥ 120
Temperature ($^{\circ}\text{C}$)	N/A	Value $\geq 38.3^{\circ}\text{C}$ and $\geq 0.8^{\circ}\text{C}$ increase from Baseline

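### The renal markedly abnormal counts in SAP Table 6.2 ignore each subject's baseline, and no planned table counts subjects whose creatinine clearance stage worsened

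*SAP*

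**What the plan says.** SAP 6.8.2 defines the markedly abnormal summary by any value after baseline: "The number and percentage of subjects with post-baseline results qualifying as markedly abnormal will be summarized by parameter". Table 6.2 gives fixed limits. For creatinine there is an upper limit of 177 µmol/L. For clearance the row reads "Creatinine clearance ml/min ≤60 NA". Neither row has a baseline condition.

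The same section plans other renal outputs:

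- Serum chemistry and creatinine clearance are summarized by visit, and "Both actual values and change from baseline will be summarized".
- Shift tables cross-classify low, normal and high from baseline to each later visit and to end of treatment (EOT), among subjects with both values.
- All laboratory data are listed.
- "Estimated creatinine clearance rate will be re-calculated based on the Cockcroft-Gault (C-G) equation", and the result is summarized by the stages in Table 6.1. No shift from baseline stage is specified. Table 6.1 places 60 to 89 mL/min in stage 2, "Mild decrease in GFR".

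Elsewhere the SAP does use baseline. The systolic pressure rule in Table 6.4 is "A decrease from Baseline of ≥ 20 to a value ≤ 90", and Table 6.3 includes increases in QTc from baseline.

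SAP 5.3.2 defines baseline as the REPLACE baseline for subjects who completed REPLACE, with or without RELAY, and as the RELAY baseline for those who completed RELAY only. The only renal entry criterion in Protocol 4.2 is creatinine below 1.5 mg/dL, applied at RACE enrollment.

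**The concern.** Long-term safety is the primary objective, and creatinine clearance is a named safety endpoint (Protocol 2.3.1, SAP 4.5). The protocol describes the renal risk itself: "substantial amounts of calcium can be lost leading to hypercalciuria with the attendant risks of nephrocalcinosis, hematuria and renal dysfunction". Treatment may last up to 80 months in about 50 subjects with no control arm, so the natural comparator for each subject is his or her own baseline.

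Fixed limits do not use that comparator, and the two renal lines err in opposite directions. The creatinine line needs a large loss of function before it counts anyone with a low starting value. The clearance line counts anyone at or below 60, including subjects who were there before treatment. A reader of the clinical study report could not tell from these two lines how many subjects got worse.

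**Working it through.** **Inputs.** The limits are from SAP Table 6.2 and the stages from Table 6.1. The formula is the SAP's: CLcr = (140 − age) × weight × (0.85 if female) / (72 × creatinine in mg/dL). The unit conversion is the standard 88.4 µmol/L per mg/dL. Ages, weights, creatinine values and counts in the examples are assumptions, because the documents give no distribution for them. The plan states no renal event rate, so there is no figure to reproduce.

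**1. The creatinine limit.** 177 / 88.4 = 2.00 mg/dL. At fixed age and weight, the CLcr loss needed to reach it from a starting value b is 1 − b/2.00:

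- b = 0.8: 60%
- b = 1.0: 50%
- b = 1.2: 40%

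**2. Counted without any change.** These subjects all have creatinine below 1.5 mg/dL:

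- Woman, 60 years, 60 kg, 1.1 mg/dL: 80 × 60 × 0.85 / (72 × 1.1) = 51.5 mL/min.
- Woman, 65 years, 60 kg, 1.4 mg/dL: 75 × 60 × 0.85 / (72 × 1.4) = 37.9 mL/min.
- Man, 70 years, 60 kg, 1.0 mg/dL: 70 × 60 / 72 = 58.3 mL/min.

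Each meets the clearance limit at any post-baseline visit where nothing has changed.

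**3. Not counted despite a large fall.**

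- Man, 45 years, 85 kg, from 0.9 to 1.6 mg/dL: 95 × 85 / (72 × 0.9) = 124.6, then 95 × 85 / (72 × 1.6) = 70.1 mL/min, a fall of 44%.
- Woman, 40 years, 75 kg, from 0.6 to 1.0 mg/dL: 100 × 75 × 0.85 / (72 × 0.6) = 147.6, then 100 × 75 × 0.85 / 72 = 88.5 mL/min, a fall of 40%.

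Both stay above 60 mL/min and below 2.00 mg/dL, so neither is in the table. Both move from stage 1 to stage 2, so a stage-shift table would show them.

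**4. Age alone.** If age is updated at each visit and creatinine and weight stay constant, CLcr falls by (80/12)/(140 − age) over 80 months. That is 6.67/95 = 7.0% from age 45 and 6.67/80 = 8.3% from age 60. A starting value of 62 becomes 57.6 or 56.8 and crosses the limit.

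**5. Effect on the reported percentage.** Suppose 50 subjects, 5 who newly reach 60 or less, and k who were there at baseline and stay there. The SAP count is (5 + k)/50. New onset among those at risk is 5/(50 − k).

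- k = 0: 10% and 10%
- k = 5: 20% and 11.1%
- k = 10: 30% and 12.5%
- k = 15: 40% and 14.3%

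**6. What the other planned outputs add.** Mean change by visit describes the group and does not count individuals. Shift tables count individuals, but only when they cross a normal range. The documents give no normal range for a calculated CLcr, so it is unclear whether that shift table can be built. A creatinine shift table might catch the man in step 3 but could miss the woman, depending on a laboratory range that is not given. Stage summaries without baseline stage show how many subjects are in each stage, not how many moved.

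**The case against.** A reader might infer that new renal decline goes unmeasured, or that there is no valid count of any kind. The documents do not support that. SAP 6.8.2 plans change from baseline by visit, shift tables from baseline to each visit and EOT, and full listings. With about 50 subjects the listings can be read one by one. Clinically significant laboratory changes are also adverse events (Protocol 6.2.1 and 6.2.3) and are counted per subject in SAP 6.8.1, though that route rests on investigator judgement. All of this stands and narrows the point to a missing subject-level table.

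A reader might also infer that the creatinine limit lies at least a third above every baseline, since 2.00/1.5 = 1.33. That does not follow. The 1.5 mg/dL criterion applies at RACE enrollment, whereas the analysis baseline for roll-over subjects comes from REPLACE or RELAY, and the criterion does not bound that value.

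Two further objections are fair. Every row in Table 6.2 is a fixed limit, and Table 6.3 also has fixed limits of 500 ms. Table 6.2 is thus a general screen, and the contrast with Table 6.4 shows a better option within the SAP, not a mistake. Second, counting subjects who were already at 60 or less overstates harm; it does not hide it, and the clearance line will catch some falls that the creatinine line misses. The mixed count still cannot be read as an incidence, and step 3 shows falls of 40% or more that neither line records.

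**Conclusion.** The point holds in a limited form. The two renal counts in Table 6.2 are not referenced to baseline. The clearance count combines existing and new cases, and substantial individual falls can meet neither limit. The planned change, shift and listing outputs cover part of the gap, but no table counts subjects whose CLcr stage worsened.

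The unit conversion and the Cockcroft-Gault results are exact for the inputs shown. The size of the distortion is unknown, because the documents do not say how many subjects had CLcr of 60 or less at the analysis baseline. It is nil if none did. In the assumed example it is 20% to 40% reported against 11% to 14% for new onset. No population percentage should be quoted as an estimate for this trial.

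A minor related point: exactly 60 mL/min is a mild decrease in Table 6.1 and markedly abnormal in Table 6.2.

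**What to change.** In SAP 6.8.2, keep the existing limits and make these changes:

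- Report CLcr of 60 mL/min or less as new onset, with subjects above 60 at the analysis baseline of SAP 5.3.2 as the denominator. Show those at 60 or less at baseline in a separate row.
- Add a shift table of Table 6.1 stage from baseline to the worst post-baseline value and to EOT.
- Align the value of exactly 60 between Tables 6.1 and 6.2. State the rounding as well, since a calculated value between 59 and 60 or between 89 and 90 falls in no stage as written.
- State whether age and weight are updated at each visit in the formula. New onset will still include subjects who cross 60 through the age term.
- Optionally, add one line for percentage change from baseline in creatinine or CLcr, with a threshold chosen and justified by the sponsor. The documents give no basis for a particular value.

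The cost is SAP wording and one or two extra tables. Clearance is already scheduled at baseline, Weeks 16, 32 and 52, every 4 months in the extension and at end of treatment. The new-onset figure may be lower than the current clearance count, and the stage shift may show declines that the current tables leave unseen.
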